#### 8.1.1 Visit Schedule and Assessments

The Trial Flowchart, Schema, and Schedule of Events table are found in Section 1. All study procedures will be performed by the investigator or a suitably qualified designee.

##### 8.1.1.1 Visit 1 (Screening)

The following procedures will be performed:

- Review the study and procedures, provide the patient with the opportunity to review the consent form ask questions, and have their questions answered.
- Obtain written informed consent and document in the subject's chart
- Collect patient demographics, medical history including concomitant medications

- For women of childbearing potential, confirm adequacy of birth control methods and document in the subject's medical record
- Perform standard physical exam
- Perform MQT
- Order allergen specific serum IgE testing
- Collect vital signs, including heart rate, blood pressure, and respiration
- Confirm patient eligibility by assessing whether the patient satisfies the study inclusion and exclusion criteria
- Prescribe symptomatic treatment / rescue medications including an intranasal corticosteroid and oral antihistamine
- Randomize patient using the on-line EDC system and label the assigned vial for individual patient use
- Complete entry of patient information into the EDC system (eCRF)

#### 8.1.1.2 Visit 2 (Treatment Visit 1)

The following procedures will be performed:

- For women of childbearing potential, perform a urine pregnancy test to confirm continued eligibility for the study
- Collect vital signs
- Review ILIT procedure, allow patient to ask and have questions answered
- Perform ILIT procedure following the procedures outlined in detail in section 6.1.2:
  - Identify and select a right-sided superficial inguinal lymph node using ultrasonography
  - Prepare the area for aseptic injection
  - Verify assignment of the subject's assigned vial of allergenic extract or matched placebo
  - Inspect vial for clarity or discoloration
  - For hypersensitive patients, prepare a 1:10 dilution using aseptic procedures from the assigned vial and standard Allergenic Extract diluent (phenol-saline), as described in Section 6.2
  - Draw 0.1 mL of allergenic extract from the vial or the 1:10 dilution, as appropriate using a 1 mL syringe.
  - Tighten the patient's skin around the lymph node using thumb, index finger, and middle finger to pull skin taut and allow for controlled placement of the injection volume.
  - Using a sterile 25-gauge or smaller needle, approach the lymph node with the needle at a 90° angle to the skin
  - Insert the needle into the selected lymph node and aspirate the syringe by pulling the plunger slightly to avoid accidental intravenous administration
    - If blood is drawn up, discard and replace the syringe and extract, prepare a new syringe and repeat
  - Slowly inject into the entire volume into the lymph node and during injection, observe the lymph node volume through the skin to confirm injection by visible enlargement.
  - Administer a sterile dressing, if necessary
  - Record injection information in the patient's medical chart

- Collect vital signs every fifteen minutes for one hour (60 minutes) post-injection
- Collect patient-reported pain immediately after and 30 minutes post-injection using the NRS-11
- Record any local or systemic reactions on the TSS worksheet
  - Patients that are stable and do not have any evidence of a systemic reaction will be monitored in the office for sixty (60) minutes post-injection
  - Patients that experience a systemic reaction or other serious, treatment-emergent adverse event will remain in the office for observation until stable
- Administer rescue medications, if necessary, according to the procedures in section 2.3.1
- Schedule the next visit
- Complete entry of patient information into the EDC system (eCRF)

### 8.1.1.3 Visit 3 (Treatment Visit 2)

The following procedures will be performed:

- For women of childbearing potential, perform a urine pregnancy test to confirm continued eligibility for the study
- Collect vital signs
- Assess patient for any changes to medical history, including adverse events since the previous visit, resolution of ongoing adverse events from Visit 1, or changes in concomitant medication use
- Perform ILIT procedure following the procedures outlined in detail in section 6.1.2:
  - Identify and select a right-sided superficial inguinal lymph node using ultrasonography
  - Prepare the area for aseptic injection
  - Verify assignment of the subject's assigned vial of allergenic extract or matched placebo
  - Inspect vial for clarity or discoloration
  - For patients that experienced a reaction at a prior injection, prepare a 1:10 or 1:100 dilution using aseptic procedures from the assigned vial and standard Allergenic Extract diluent (phenol-saline), as described in Section 6.2
  - Draw 0.1 mL of allergenic extract from the vial or the 1:10 dilution, as appropriate using a 1 mL syringe.
  - Tighten the patient's skin around the lymph node using thumb, index finger, and middle finger to pull skin taut and allow for controlled placement of the injection volume.
  - Using a sterile 25-gauge or smaller needle, approach the lymph node with the needle at a 90° angle to the skin
  - Insert the needle into the selected lymph node and aspirate the syringe by pulling the plunger slightly to avoid accidental intravenous administration
    - If blood is drawn up, discard and replace the syringe and extract, prepare a new syringe and repeat
  - Slowly inject into the entire volume into the lymph node and during injection, observe the lymph node volume through the skin to confirm injection by visible enlargement.
  - Administer a sterile dressing, if necessary
  - Record injection information in the patient's medical chart
- Collect vital signs every fifteen minutes for one hour (60 minutes) post-injection

- Collect patient-reported pain immediate after and 30 minutes post-injection using the NRS-11
- Record any local or systemic reactions on the TSS worksheet
  - Patients that are stable and do not have any evidence of a systemic reaction will be monitored in the office for sixty (60) minutes post-injection
  - Patients that experience a systemic reaction or other serious, treatment-emergent adverse event will remain in the office for observation until stable
- Administer rescue medications, if necessary, according to the procedures in section 2.3.1
- Schedule the next visit
- Complete entry of patient information into the EDC system (eCRF)

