Dilution to 1/100th the maximal SCIT dose will be performed in pharmacy by an unblinded pharmacist who will prepare three vials, one for each clinic location, to be distributed to and stored on-site at the clinic pharmacies at the Texan Allergy & Sinus Center locations in Austin, Dallas, and San Antonio, Texas. Extracts for this study will be prepared at a 1/100th concentration of active allergenic extract with diluent and another three vials of diluent with a matched concentration of glycerin. After visually confirming that the active group and placebo group are visually identical, the lots of investigational product will be labeled and securely stored under the control of the unblinded pharmacist only. Once patients are enrolled, the unblinded pharmacist will request the treatment assignment via the EDC system and prepare a patient-specific vial with the correct active or control solution. The vial will be labeled for the individual patient's use according to the clinic and pharmacy SOPs for preparation and storage of allergenic extracts. Patient-assigned vials will be retained in the pharmacy in secure storage, separate from the unblinded solutions for the duration of the study according to the TASC's SOPs for storage of AIT vials and consistent with the AAAAI Practice Management Resource Guide, 2014 edition, Allergen Immunotherapy Extract Preparation Manual. Records of dilution, mixing and administration of extracts will be maintained in accordance with the clinic and pharmacy SOPs. Subsequent dilutions prepared according to the patient-specific dosing regimen in section 6.2 will be made by the investigator (blind to the actual contents of the vial) immediate before performing the injection procedure.

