### 6.2.4 PREPARATION

Preparation of syringes and, if necessary patient-specific extract dilutions will follow TASC's SOPs and the AAAAI Practice Management Resource Guide, 2014 edition, Allergen Immunotherapy Extract Preparation Manual. Specifically, bulk extracts will be diluted at the investigational drug pharmacy at a standard 1:100th dilution using Sterile Diluent for Allergenic Extracts. Dilutions will be made with sterile disposable syringes using aseptic technique using two sequential, 10-fold dilution processes to achieve the desired concentration for initiation and continuation of immunotherapy. For example, transferring 0.5 mL of a 10,000 PNU/mL extract into 4.5 mL of diluent will yield 5 mL of extract at 1,000 PNU/mL. For weight volume products, a 1:100 w/v dilution may be prepared from a 1:10 w/v by transferring 0.5 mL of the 1:10 w/v to 4.5 mL of diluent. Prepare as many additional serial dilutions as necessary to reach the appropriate concentration.

For patients that display a hypersensitivity reaction to the extract, as defined in section 5.2 (a wheal for allergenic extract greater than that for the positive control), the initial dose will be at an additional 1:10 dilution. For patients that experience a systemic reaction to any ILIT injection, as defined in section 2.3.2, subsequent ILIT injections will be made at a 1:10 dilution from the preceding treatment. Thus, the dosing will be as follows:

Baseline	Not Hypersensitive to Allergenic Extract on MQT				IS HYPERSENSITIVE to Allergenic Extract on MQT			
Injection 1	Inject 0.1 mL of undiluted IP				Inject 0.1 mL of 1:10 diluted IP			
Injection 2	No Systemic Reaction at Injection 1 Inject 0.1 mL of undiluted IP		SYSTEMIC REACTION at Injection 1 Inject 0.1 mL of 1:10 diluted IP		No Systemic Reaction at Injection 1 Inject 0.1 mL of 1:10 diluted IP		SYSTEMIC REACTION at Injection 1 Inject 0.1 mL of 1:100 diluted IP	

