Injection 3	No Systemic Reaction at Injection 2 Inject 0.1 mL of undiluted IP	SYSTEMIC REACTION at Injection 2 Inject 0.1 mL of 1:10 diluted IP	No Systemic Reaction at Injection 2 Inject 0.1 mL of 1:10 diluted IP	SYSTEMIC REACTION at Injection 2 Inject 0.1 mL of 1:100 diluted IP	No Systemic Reaction at Injection 2 Inject 0.1 mL of 1:10 diluted IP	SYSTEMIC REACTION at Injection 2 Inject 0.1 mL of 1:10 diluted IP	No Systemic Reaction at Injection 2 Inject 0.1 mL of 1:100 diluted IP	SYSTEMIC REACTION at Injection 2 Inject 0.1 mL of 1:1,000 diluted IP

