### 6.3 MEASURES TO MINIMIZE BIAS: RANDOMIZATION AND BLINDING

Once enrollment, subjects in this study will be randomized in a 1:1 ratio to receive either ILIT with 1:100 diluted Mountain Cedar pollen allergenic extract or diluent as placebo control. Preparation of the diluted allergenic extract or placebo will be performed by the pharmacy according to the procedures defined in Section 6.2. Neither the patient nor the investigator will know the treatment assignment. Randomization information will be stored in the EDC system. Emergency unblinding is unlikely to be required. Patients receiving AIT are at risk of systemic hypersensitivity reactions and such reactions will be treated according to the procedures outlined in Section 2.3.1 regardless of treatment assignment. Blinding may be imperfect in cases where strong systemic reactions occur, but in previous trials of AIT, injection site reactions and systemic reactions, including anaphylaxis have been reported to occur in both groups, but at a lower rate in the placebo group. Thus, this risk of unblinding due to obvious treatment-related side effects is possible, but not definitive. Dose adjustments will be made by serial dilution following the procedures outlined in Section 6.2 and do not require knowledge of the treatment assignment. The end-of-study assessment will include a question for subjects regarding their belief about which treatment they received. This will be used to assess the maintenance of the study blind.

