#### 8.1.1.4 Visit 4 (Treatment Visit 3)

The following procedures will be performed:

- For women of childbearing potential, perform a urine pregnancy test to confirm continued eligibility for the study
- Collect vital signs
- Assess patient for any changes to medical history, including adverse events since the previous visit, resolution of ongoing adverse events from Visit 2, or changes in concomitant medication use
- Perform ILIT procedure following the procedures outlined in detail in section 6.1.2:
  - Identify and select a right-sided superficial inguinal lymph node using ultrasonography
  - Prepare the area for aseptic injection
  - Verify assignment of the subject's assigned vial of allergenic extract or matched placebo
  - Inspect vial for clarity or discoloration
  - For patients that experienced a reaction at a prior injection, prepare a 1:10 or 1:100 dilution using aseptic procedures from the assigned vial and standard Allergenic Extract diluent (phenol-saline), as described in Section 6.2
  - Draw 0.1 mL of allergenic extract from the vial or the 1:10 dilution, as appropriate using a 1 mL syringe.
  - Tighten the patient's skin around the lymph node using thumb, index finger, and middle finger to pull skin taut and allow for controlled placement of the injection volume.
  - Using a sterile 25-gauge or smaller needle, approach the lymph node with the needle at a 90° angle to the skin
  - Insert the needle into the selected lymph node and aspirate the syringe by pulling the plunger slightly to avoid accidental intravenous administration
    - If blood is drawn up, discard and replace the syringe and extract, prepare a new syringe and repeat
  - Slowly inject into the entire volume into the lymph node and during injection, observe the lymph node volume through the skin to confirm injection by visible enlargement.
  - Administer a sterile dressing, if necessary
  - Record injection information in the patient's medical chart
- Collect vital signs every fifteen minutes for one hour (60 minutes) post-injection
- Collect patient-reported pain immediate after and 30 minutes post-injection using the NRS-11

- Record any local or systemic reactions on the TSS worksheet
  - Patients that are stable and do not have any evidence of a systemic reaction will be monitored in the office for sixty (60) minutes post-injection

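### The injection 2 and 3 checklists omit the 1:10 preparation for skin-test-hypersensitive patients who have not reacted, and one injection 3 cell in the Section 6.2.4 table contradicts the step-down rule

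*Protocol*

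**What the plan says.** Protocol Section 6.2.4 has three elements.

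- **Starting reduction.** For a patient whose allergen wheal exceeds that of the positive control, "the initial dose will be at an additional 1:10 dilution".
- **Step-down rule.** After a systemic reaction to any injection, "subsequent ILIT injections will be made at a 1:10 dilution from the preceding treatment".
- **Dosing table.** It has one column path for each combination of MQT status and reactions at injections 1 and 2. A hypersensitive patient without a systemic reaction stays at 1:10 at injections 2 and 3.

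The visit checklists turn this into steps.

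- **Section 8.1.1.2 (injection 1):** "For hypersensitive patients, prepare a 1:10 dilution using aseptic procedures from the assigned vial".
- **Sections 8.1.1.3 and 8.1.1.4 (injections 2 and 3):** the only dilution step reads "For patients that experienced a reaction at a prior injection, prepare a 1:10 or 1:100 dilution using aseptic procedures". It is followed by "Draw 0.1 mL of allergenic extract from the vial or the 1:10 dilution, as appropriate using a 1 mL syringe".

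Two other sections point back to the table's section. Section 6.2.1 says "Subsequent dilutions prepared according to the patient-specific dosing regimen in section 6.2 will be made by the investigator", and Section 6.3 says "Dose adjustments will be made by serial dilution following the procedures outlined in Section 6.2".

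**The concern.** The investigator makes these dilutions at the visit, just before injecting, so the checklist is the working document. A skin-test result is not a reaction at a prior injection, and Section 8.1.1.2 treats hypersensitivity as a trigger of its own. That trigger disappears after injection 1. A hypersensitive patient who tolerated the first 1:10 dose therefore meets no preparation step at injections 2 and 3. Read literally, the checklist leaves only the assigned vial.

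The second problem lies within Section 6.2.4. One injection 3 cell sends a hypersensitive patient who has just reacted to 1:10 back to 1:10.

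The lower dose for these patients is a central safety control. Section 2.2 describes an earlier ILIT pilot study in which systemic reactions followed doses at concentrations giving an allergen-to-histamine wheal ratio above 1. Its authors advised lower concentrations in such patients. Section 5.2 uses the same ratio to define hypersensitivity here.

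**Working it through.** **Inputs.** Strengths are relative to the assigned vial (undiluted IP = 1). The rule from the 6.2.4 prose is:

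- start at 1 if not hypersensitive, or 1/10 if hypersensitive;
- divide by 10 after each systemic reaction;
- otherwise keep the previous strength.

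**Step 1: rule against table, injection 2.** The rule gives undiluted, 1:10, 1:10 and 1:100. The table prints the same, so 4 of 4 cells agree.

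**Step 2: rule against table, injection 3.** Cells are in printed order.

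| Cell | MQT status | Reaction at 1 | Reaction at 2 | Rule | Table |
|---|---|---|---|---|---|
| 1 | Not hypersensitive | No | No | undiluted | undiluted |
| 2 | Not hypersensitive | No | Yes | 1:10 | 1:10 |
| 3 | Not hypersensitive | Yes | No | 1:10 | 1:10 |
| 4 | Not hypersensitive | Yes | Yes | 1:100 | 1:100 |
| 5 | Hypersensitive | No | No | 1:10 | 1:10 |
| **6** | **Hypersensitive** | **No** | **Yes** | **1:100** | **1:10** |
| 7 | Hypersensitive | Yes | No | 1:100 | 1:100 |
| 8 | Hypersensitive | Yes | Yes | 1:1,000 | 1:1,000 |

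Seven of 8 agree. Cell 6 prints "SYSTEMIC REACTION at Injection 2 Inject 0.1 mL of 1:10 diluted IP", which is the strength that caused the reaction. It cannot be read as a further 1:10 relative to the previous dose, because cells 4 and 8 (1:100 and 1:1,000) are stated relative to the vial. The ratio of table dose to rule dose is (1/10) / (1/100) = 10.

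**Step 3: checklists against the 12 printed cells for injections 2 and 3.**

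| Checklist coverage | Cells | Count |
|---|---|---|
| Preparation and draw both covered | Injection 2: not hypersensitive, with or without reaction. Injection 3: cells 1, 2, 3, 6 | 6 |
| No preparation step triggered | Hypersensitive non-reactor at injection 2. Injection 3: cell 5 | 2 |
| Strength not listed for preparation (1:1,000) | Injection 3: cell 8 | 1 |
| 1:100 listed for preparation, not named in the draw step | Injection 2: hypersensitive reactor. Injection 3: cells 4, 7 | 3 |

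If cell 6 is corrected to 1:100 it moves to the last row, and the counts become 5, 2, 1 and 4.

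**Step 4: dose consequence for a hypersensitive non-reactor in the active arm.**

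- Per injection: 1 / (1/10) = 10-fold at each of injections 2 and 3.
- Over the series, literal checklist: 0.1 + 1 + 1 = 2.1 undiluted doses.
- Over the series, table: 0.1 + 0.1 + 0.1 = 0.3.
- Ratio: 2.1 / 0.3 = 7.

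**Step 5: trigger wording.** The checklists act on any reaction; 6.2.4 acts on a systemic one. A purely local reaction could therefore lead to a dilution that 6.2.4 does not call for.

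**The case against.** The strongest reply is that the missing step is an omission and not a conflict. Nothing tells staff to give undiluted product to a hypersensitive patient. The table states 1:10, Sections 6.2.1 and 6.3 send dose adjustments to Section 6.2, and the draw line still mentions a 1:10 dilution. This stands as far as it goes: the right dose can be found. But the draw line selects a preparation and does not create one, and the checklist's own reference to Section 6.2 sits inside a step this patient does not trigger.

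Several points of scale are also fair.

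- Undiluted IP is already 1/100 of the maximal subcutaneous dose (Section 6.2.1) and is the standard dose for other patients.
- The 7-fold figure needs the same error at two visits, after a correct injection 1.
- The 1:1,000 path needs two systemic reactions in one patient and is remote.
- The wider trigger in Step 5 errs towards caution.
- The table already shows the 1:10 carrying forward, so a sentence saying so only makes the prose explicit.

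On cell 6, other safeguards exist. Section 8.2 puts the study on hold after a treatment-related grade 3 systemic reaction or a related serious event. Section 2.3.1 calls for at least a 50% cut after a severe systemic reaction. SAP Section 10 mentions a stopping rule at two systemic reactions. None of these settles the dose after a single mild (WAO grade 1/2) systemic reaction. There the prose and the table give different answers, and referring to Section 6.2 cannot help.

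**Conclusion.** Both faults hold. The injection 2 and 3 checklists contain no step that prepares the 1:10 dose for a hypersensitive patient who has not reacted; this is a risk of a 10-fold overdose at each injection. In addition, 1 of the 12 table cells gives ten times the dose that the protocol's own rule allows, to a hypersensitive patient who has just reacted. The gaps at 1:100 and 1:1,000 and the looser trigger are lesser faults in the same steps. Because these concern allergen dose in the patients identified as most sensitive, they must be fixed.

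The conclusion rests on three things:

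- The table's eight injection 3 cells were extracted in the right order. They are complete and coherent, but cell 6 should be checked against the PDF.
- The dose consequences apply only to the active arm.
- The number of hypersensitive patients is not given, so the number exposed cannot be stated.

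No sample size, power or error rate depends on this point.

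**What to change.** 1. In Sections 8.1.1.3 and 8.1.1.4, trigger the dilution step for patients who are hypersensitive on the MQT or who had a systemic reaction at a prior injection.
2. In the same sections, have staff prepare and draw the strength given by the 6.2.4 table, including 1:100 and 1:1,000, and record the strength used.
3. Before the checklists rely on the table, change injection 3 cell 6 (hypersensitive, first reaction at injection 2) from 1:10 to 1:100.
4. Add a sentence to 6.2.4 saying that the hypersensitivity reduction applies to all three injections.
5. If dosing is complete, as the past tense in SAP Sections 2.2.1 and 6.2 suggests, items 1 to 4 can no longer protect these participants. In that case, verify from the injection records, and report, the dilution each hypersensitive patient received at injections 2 and 3. The planned outputs do not ask for this: the compliance listing in SAP Section 8.6 covers visits, dates and windows, and Protocol Section 9.4.8 tabulates individual dose only for serious adverse events of interest.

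The cost is wording in two checklists, one sentence and one table cell, or a record check for the hypersensitive patients among at most 32 enrolled. No extra visits or patients are needed.

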#### 8.1.1.4 Visit 4 (Treatment Visit 3)

The following procedures will be performed:

- For women of childbearing potential, perform a urine pregnancy test to confirm continued eligibility for the study
- Collect vital signs
- Assess patient for any changes to medical history, including adverse events since the previous visit, resolution of ongoing adverse events from Visit 2, or changes in concomitant medication use
- Perform ILIT procedure following the procedures outlined in detail in section 6.1.2:
  - Identify and select a right-sided superficial inguinal lymph node using ultrasonography
  - Prepare the area for aseptic injection
  - Verify assignment of the subject's assigned vial of allergenic extract or matched placebo
  - Inspect vial for clarity or discoloration
  - For patients that experienced a reaction at a prior injection, prepare a 1:10 or 1:100 dilution using aseptic procedures from the assigned vial and standard Allergenic Extract diluent (phenol-saline), as described in Section 6.2
  - Draw 0.1 mL of allergenic extract from the vial or the 1:10 dilution, as appropriate using a 1 mL syringe.
  - Tighten the patient's skin around the lymph node using thumb, index finger, and middle finger to pull skin taut and allow for controlled placement of the injection volume.
  - Using a sterile 25-gauge or smaller needle, approach the lymph node with the needle at a 90° angle to the skin
  - Insert the needle into the selected lymph node and aspirate the syringe by pulling the plunger slightly to avoid accidental intravenous administration
    - If blood is drawn up, discard and replace the syringe and extract, prepare a new syringe and repeat
  - Slowly inject into the entire volume into the lymph node and during injection, observe the lymph node volume through the skin to confirm injection by visible enlargement.
  - Administer a sterile dressing, if necessary
  - Record injection information in the patient's medical chart
- Collect vital signs every fifteen minutes for one hour (60 minutes) post-injection
- Collect patient-reported pain immediate after and 30 minutes post-injection using the NRS-11

- Record any local or systemic reactions on the TSS worksheet
  - Patients that are stable and do not have any evidence of a systemic reaction will be monitored in the office for sixty (60) minutes post-injection
  - Patients that experience a systemic reaction or other serious, treatment-emergent adverse event will remain in the office for observation until stable
- Administer rescue medications, if necessary, according to the procedures in section 2.3.1
- Instruct patient on completion of daily symptom and medication diary, reconfirm contact information for e-diary distribution
- Complete entry of patient information into the EDC system (eCRF)

